### 219238 (RSV OA=ADJ-018) Protocol Final

Type of contact	Visit 1	Visit 2	Visit 3	Visit 4	Notes	
Timepoint	Day 1	Day 31	Month 6	Month 12		
Study intervention		 				
Check criteria for temporary delay for enrollment and study intervention administration	0				See Section 5.5	
Urine pregnancy test (only for women of childbearing potential in Cohort 1)	●p				See Section 8.2.1.7	
Study group and intervention number allocation	0				See Section 6.3.2 and Section 6.3.3	
Record body temperature before study intervention administration	•				The route for measuring temperature can be oral or axillary (see Section 8.2.1.8). Fever is defined as temperature ≥38.0°C/100.4°F regardless of the location of measurement.	
Study intervention administration (including 30-minutes post-study intervention administration observation)	•				See Section 6.1	
Record administered study intervention number	•					
Safety assessments						
Distribute diary cards	0				A paper diary will be distributed to all study participants at Visit 1 (day of study intervention administration). All participants will record solicited events after study intervention administration and for 3 subsequent days (Days 1-4), unsolicited AEs, and concomitant medications/products after study intervention administration and for 29 subsequent days (Days 1-30). See Section 10.3.8	
Return of diary cards		0			See Section 10.3.8	
Record solicited administration site and systemic events (Days 1–4 post-study intervention administration)	•	•			See Section 10.3.8 and Table 11	
Record unsolicited AEs (Days 1-30 post-study intervention administration) in the participants c	•	•			See Section 10.3.8 and Table 11	
Record concomitant medications/vaccinations	•	•	•	•	See Section 6.8	
Record any intercurrent medical conditions	•	•	•	•	See Section 9.2.1 and Table 11	
Record all SAEs and pIMDs c	•	•	•		See Section 10.3.8 and Table 11	
Record AEs/SAEs leading to withdrawal from the study and pregnancies	•	•	•	•	See Section 10.3.8 and Table 11	

219238 (RSV OA=ADJ-018) Protocol Final

Type of contact	Visit 1	Visit 2	Visit 3	Visit 4	Notes
Timepoint	Day 1	Day 31	Month 6	Month 12	

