Record SAEs related to study participation, or to a concurrent GSK medication/vaccine	•	•	•	•	SAEs related to study participation, or to a concurrent GSK medication/vaccine should be collected from the time of consent obtained (prior to administration of the study intervention) up to study end.  See Section 10.3.8 and Table 11
Record SAEs and pIMDs related to study intervention administration and fatal SAEs c	•	•	•	•	SAEs and pIMDs related to study intervention administration and fatal SAEs should be collected after study intervention administration (Day 1) up to study end.  See Section 10.3.8 and Table 11
Study Conclusion				•	See Section 4.4

Note: The double-line borders indicate the analyses which will be performed on all data (i.e., data that are as clean as possible) obtained up to this timepoints.

AE=Adverse event; **AESI= Adverse event of specific interest**; CMI=Cell-mediated immunity; COVID-19=Coronavirus disease 2019; eCRF=Electronic case report form; pIMD=Potential immune-mediated disease; SAE=Serious adverse event.

- is used to indicate a study procedure that requires documentation in the individual eCRF
- o is used to indicate a study procedure that does not require documentation in the individual eCRF
- a. If deemed necessary by the investigator.
- b. The blood sample and urine sample for pregnancy test should be taken on the same day, prior to study intervention administration. If the study intervention administration is delayed by any reason, in the event samples have been taken, the samples will need to be collected again on the day of study intervention administration and the first blood sample will be destroyed.
- c. Atrial fibrillation (AF) will be considered as AESI in this study and will be additionally reported in the AF follow-up questionnaire (electronic or paper) in eCRF. The collection of AF will be performed following the AE/SAE reporting periods. For AF that were reported before the implementation of this Protocol Amendment 1, additional available information should be encoded in the specific AF follow-up questionnaire retrospectively.

Note: Visit 2, Visit 3 and Visit 4 should be done on site. Under special circumstances (e.g., pandemic), study visits can be done at home, or biological samples can be taken at a different location (see Section 8).

Table 2 Intervals between study visits

Interval	Planned visit interval	Allowed interval range
Visit 1→Visit 2	30 days	30-42 days
Visit 1→Visit 3	180 days	180-210 days

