
 
To demonstrate the NI** of the humoral immune response in participants 50-59 YOA at increased risk of RSV-LRTD compared to OA (≥60 YOA) for the RSV-B strain after RSVPreF3 OA investigational vaccine administration.
 
	
 
RSV-B neutralization titers expressed as group GMT ratio (OA-RSV/Adults-AIR-RSV), 1 month after the RSVPreF3 OA investigational vaccine administration***.
 
RSV-B neutralization-titers expressed as group SRR difference (OA-RSV - Adults-AIR-RSV), 1 month after the RSVPreF3 OA investigational vaccine administration compared to baseline***.
 
			
Secondar	y - Safety			
To evaluate the safety and reactogenicity after the RSVPreF3 OA investigational vaccine administration.	
 
Percentage of participants reporting each solicited administration site event with onset within 4 days after study intervention administration (i.e., the day of study intervention administration and 3 subsequent days).
 
Percentage of participants reporting each solicited systemic event with onset within 4 days after study intervention administration (i.e., the day of study intervention administration and 3 subsequent days).
 
Percentage of participants reporting unsolicited AEs within 30 days after study intervention administration (i.e., the day of study intervention administration and 29 subsequent days).
 
Percentage of participants reporting any SAEs and pIMDs after study intervention administration (Day 1) up to Month 6.
 
Percentage of participants reporting SAEs and pIMDs related to study intervention administration after study intervention administration (Day 1) up to study end (Month 12).
 
Percentage of participants reporting any fatal SAEs after study intervention administration (Day 1) up to study end (Month 12).
 
			
Secondary - In	nmunogenicity			
To evaluate the humoral immune response to the RSVPreF3 OA investigational vaccine until 12 months post-study intervention administration.	RSV-A and RSV-B neutralization-titers expressed as GMT, at pre-study intervention administration, 1 month, 6 months and at 12 months after study intervention administration.			

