Systemic Scleroderma (Systemic Sclerosis)	Includes Reynolds syndrome (RS), systemic sclerosis with diffuse scleroderma and systemic sclerosis with limited scleroderma (also known as CREST syndrome)
Neuroinflammatory/neuromuscular	disorders
Acute disseminated	Includes the following:
encephalomyelitis (ADEM) and	Acute necrotizing myelitis
	 

25 May 2023

219238 (RSV OA=ADJ-018) Protocol Final

Medical Concept	Additional Notes
other inflammatory	Bickerstaff's brainstem encephalitis
demyelinating variants	Disseminated necrotizing leukoencephalopathy (also known as Weston-Hurst syndrome, acute hemorrhagic leuko-encephalitis, or acute necrotizing hemorrhagic encephalomyelitis)
	Myelin oligodendrocyte glycoprotein antibody-associated disease
	Neuromyelitis optica (also known as Devic's disease)
	Noninfective encephalitis / encephalomyelitis / myelitis
	Postimmunization encephalomyelitis
Guillain-Barré syndrome (GBS)	Includes variants such as Miller Fisher syndrome and the acute motor and sensory axonal neuropathy (AMSAN)
Idiopathic cranial nerve	Including but not limited to:
palsies/paresis and inflammations (neuritis)	Cranial nerve neuritis (e.g., Optic neuritis)
illiallillations (neurtis)	Idiopathic nerve palsies/paresis (e.g., Bell's palsy)
	Melkersson-Rosenthal syndrome
	Multiple cranial nerve palsies/paresis
Multiple Sclerosis (MS)	Includes the following:
	Clinically isolated syndrome (CIS)
	Malignant MS (the Marburg type of MS)
	Primary-progressive MS (PPMS)
	Radiologically isolated syndrome (RIS)
	Relapsing-remitting MS (RRMS)
	Secondary-progressive MS (SPMS)
	Uhthoff's phenomenon
Myasthenia gravis	Includes ocular myasthenia and Lambert-Eaton myasthenic syndrome
Narcolepsy	Includes narcolepsy with or without presence of unambiguous cataplexy
Peripheral inflammatory	Including but not limited to:
demyelinating neuropathies and plexopathies	Acute Brachial Radiculitis (also known as Parsonage-Turner Syndrome or neuralgic amyotrophy)
	Antibody-mediated demyelinating neuropathy
	Chronic idiopathic axonal polyneuropathy (CIAP)
	Chronic Inflammatory Demyelinating Polyradiculoneuropathy (CIDP), including atypical CIDP variants (e.g., multifocal acquired demyelinating sensory and motor neuropathy also known as Lewis-Sumner syndrome)
	Multifocal motor neuropathy (MMN)
Transverse myelitis (TM)	Includes acute partial transverse myelitis (APTM) and acute complete transverse myelitis (ACTM)
Renal disorders	

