## 10.3.8.1. Time period for collecting and recording AEs, SAEs, AESIs (including pIMDs and AF) and pregnancies (Amended: 25 May 2023)

Refer to Table 11 for an overview of the protocol required reporting periods for AEs, SAEs, pIMDs and pregnancies.

All solicited administration site and systemic events with onset during the 4 days following administration of the study intervention, and all unsolicited AEs that occur during the 30 days following administration of the study intervention must be recorded into the appropriate section of the eCRF, irrespective of their intensity.

Non-serious AF with an onset during the 30-day period following study vaccine administration will be collected.

The time period for collecting and recording all SAEs and pIMDs will begin at the first receipt of study intervention and will end 6 months after study intervention administration. *AF reporting will follow the same reporting periods as for AEs and SAEs (Table 11)*.

All AEs/SAEs/AESIs (including pIMDs and AF) leading to withdrawal from the study and pregnancies will be collected and recorded from the time of the first receipt of study intervention until the participant is discharged from the study. SAEs related to study participation or to a concurrent GSK medication/vaccine will be collected from the time consent is obtained until the participant is discharged from the study. All pIMDs related to study participation will be collected until study end.

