- The number and percentage of participants with any unsolicited AEs during the 30-day follow-up period with its exact 95% CI will be tabulated by group and by MedDRA Primary System Organ Class (SOC), High Level Term (HLT) and Preferred Term (PT). Similar tabulation will be done for Grade 3 unsolicited AEs, for any causally related unsolicited AEs, for Grade 3 causally related unsolicited AEs and for unsolicited AEs resulting in a medically attended visit. The analyses of unsolicited AEs will include SAEs, AESIs (including pIMDs and AF), unless otherwise specified.
- The number and percentage of participants with any non-serious unsolicited AEs during the 30-day follow-up period with its exact 95% CI will be tabulated by group and by MedDRA Primary System Organ Class (SOC), High Level Term (HLT) and Preferred Term (PT). Similar tabulation will be done for Grade 3 non-serious unsolicited AEs, for any causally related non-serious unsolicited AEs, for Grade 3 causally related non-serious unsolicited AEs and for non-serious unsolicited AEs resulting in a medically attended visit.
- The number and percentage of participants with any unsolicited AEs reported within 30 minutes following vaccination with its exact 95% CI will be tabulated by group and by MedDRA Primary System Organ Class (SOC), High Level Term (HLT) and Preferred Term (PT). Similar tabulation will be done for Grade 3 unsolicited AEs reported within 30 minutes following vaccination.
- The verbatim reports of unsolicited AEs, including SAE and AESI, will be reviewed by a qualified person and the signs and symptoms will be coded according to the MedDRA Dictionary for Adverse Reaction Terminology. Every verbatim term will be matched with the appropriate Preferred Term.
- The number and percentage of participants with at least one report of SAE classified by the MedDRA Primary SOC, HLT and PT from vaccination up to Month 6 will be tabulated with exact 95% CI.
- The number and percentage of participants with at least one report of SAE classified by the MedDRA Primary SOC, HLT and PT, related to study intervention administration, from vaccination up to Month 6 and study end (Month 12) will be tabulated with exact 95% CI.
- The number and percentage of participants with any fatal SAE, from vaccination up to Month 6 and study end (Month 12) will be tabulated with exact 95% CI.

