- The number and percentage of participants with at least one report of pIMD classified by the MedDRA Primary SOC, HLT and PT from vaccination up to Month 6 will be tabulated with exact 95% CI.
- The number and percentage of participants with at least one report of pIMD classified by the MedDRA Primary SOC, HLT and PT, related to study intervention administration, from vaccination up to Month 6 and study end (Month 12) will be tabulated with exact 95% CI.
- The number and percentage of participants with specific Demyelinating disorder with onset within 30 days of vaccination will be tabulated with exact 95% CI.
- The number and percentage of participants with specific Serious Demyelinating disorder from vaccination up to Month 6 and study end (Month 12) will be tabulated with exact 95% CI.
- All SAEs/AESIs (including pIMDs and AF) up to study end (Month 12) will also be described in detail in a tabular listing.
- AEs/SAEs leading to study discontinuation from vaccination up to study end will be tabulated.
- For web posting purposes, the number of occurrences and the number and percentage of participants with non-serious AEs (solicited and unsolicited combined) during the 30-day follow-up period (i.e., the day of vaccination and 29 subsequent days) will be produced by SOC and PT.
- In case of pregnancies, these will be described in detail.
- In case participants belonging to the OA stratum receive placebo (i.e., participants eliminated from the ES following code 1100, refer to Section 3.1.2), SAEs and AESIs (including pIMDs and AF) reported (if any) will be described.
- AF AESIs will be tabulated within the summary of AEs or SAEs according to their classification.

For analysis of SAEs/AESIs (including pIMD and AF) within 6 months after vaccination, the reporting period will start at vaccination and will end at Day 183 after each dose, computed as 6×30.5 days = 183 days.

Refer to Section 6.1.5 and Section 6.1.6 for the analysis of concomitant medications and concomitant vaccination.

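### The serious demyelinating disorder row runs to Month 12 without restriction, but the protocol collects all serious events only to Month 6

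*SAP*

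**What the plan says.** SAP Section 4.3.2.1 plans, per group on the Exposed Set, a row of counts and percentages worded as follows: "specific Serious Demyelinating disorder from vaccination up to Month 6 and study end (Month 12) will be tabulated with exact 95% CI". The version history shows that the demyelinating analysis came in with SAP Amendment 3, which is based on Protocol Amendment 1.

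The neighbouring rows of the same section are built differently. The all-causality SAE and pIMD rows stop at Month 6. The SAE and pIMD rows that continue to Month 12 cover only events "related to study intervention administration, from vaccination up to Month 6 and study end (Month 12) will be tabulated with exact 95% CI", and a separate row covers fatal SAEs to Month 12.

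The protocol sets the collection periods as follows:

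- Section 10.3.8.1: the period for "all SAEs and pIMDs will begin at the first receipt of study intervention and will end 6 months after study intervention administration".
- Table 1 (schedule of activities): the activity "Record all SAEs and pIMDs" is marked at Visits 1, 2 and 3 and not at Visit 4 (Month 12).
- Section 3: the corresponding secondary endpoint is the "Percentage of participants reporting any SAEs and pIMDs after study intervention administration (Day 1) up to Month 6".
- Table 1, for the period to Month 12: "SAEs and pIMDs related to study intervention administration and fatal SAEs should be collected after study intervention administration (Day 1) up to study end".
- Section 10.3.8.1, other routes open to study end: events leading to withdrawal, SAEs related to study participation or to a concurrent sponsor product, and "All pIMDs related to study participation will be collected until study end".

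Table 19 of the protocol includes demyelinating conditions among the pIMDs, for example peripheral inflammatory "demyelinating neuropathies and plexopathies".

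**The concern.** A serious demyelinating disorder is an SAE by definition, and the demyelinating conditions are on the pIMD list as well. Either way, the Month 6 limit applies, and nothing in the protocol extends it for these conditions. A serious demyelinating event after Month 6 that is judged unrelated, is not fatal, does not lead to withdrawal and is not attributed to study participation or a concurrent sponsor product need not be collected. The SAP row nevertheless counts to Month 12 over the full group denominator.

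A reader would take the result as a 12-month incidence with an exact 95% confidence interval. In a sparse safety row the upper limit is the main information, so the label matters even when the count is zero.

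Capture after Month 6 also depends largely on the investigator's causality judgement. Cohort 2 is open-label, Cohort 1 is treated as single-blind after the Day 31 analysis, and Protocol Section 6.3.5 accepts that investigators could become unblinded to some participants. Because the row is shown per group, completeness could differ between groups.

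**Working it through.** **Step 1. Compare the rows with the collection periods.**

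| SAP 4.3.2.1 row | Period tabulated | Collected in full for that period? |
|---|---|---|
| Any SAE; any pIMD | to Month 6 | Yes |
| Related SAE; related pIMD | to Month 6 and Month 12 | Yes |
| Fatal SAE | to Month 6 and Month 12 | Yes |
| Serious demyelinating disorder | to Month 6 | Yes |
| Serious demyelinating disorder | to Month 12 | No: selected categories only after Month 6 |

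The periods are taken from Protocol Table 1 and Sections 3 and 10.3.8.1. The shaded cells of Protocol Table 11 are not readable in the public text, so they are not relied on here.

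**Step 2. Length of the gap.** The SAP's Month 6 cut-off is 6 × 30.5 = 183 days, which reproduces its stated figure. Month 12 is planned at 365 days (Protocol Table 2). The period with restricted collection is 365 − 183 = 182 days, or 182/365 = 49.9% of follow-up.

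**Step 3. Possible under-count.** The documents give no event rate, so none is assumed. Assume a constant hazard, and let f be the share of post-Month 6 events that fall in a collected category. Then

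observed/true at Month 12 = (183 + 182f)/365.

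- f = 0: 183/365 = 0.50
- f = 0.5: 274/365 = 0.75
- f = 1: 365/365 = 1.00

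Over the allowed visit windows (180–210 and 350–380 days), the value at f = 0 runs from 180/380 = 0.47 to 210/350 = 0.60.

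**Step 4. Upper limit with zero events.** SAP Section 4.1.1 specifies Clopper-Pearson intervals. For 0/n the 95% upper limit is U = 1 − 0.025^(1/n). Using the planned group sizes, this gives 0.97% for n = 380 and 1.92% for n = 190.

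Under the same constant hazard, zero collected events bound the risk over an effective 183 + 182f days. The limit for a full 12 months is therefore

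1 − (1 − U)^(365/(183 + 182f)).

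| n | Printed limit (equals f = 1) | f = 0.5 | f = 0 |
|---|---|---|---|
| 380 | 0.97% | 1.28% | 1.92% |
| 190 | 1.92% | 2.55% | 3.80% |

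**Step 5. Effect of a single uncollected event.** In a group of 380 the row should read 1/380 = 0.26% (exact 95% CI 0.01% to 1.46%) but would read 0% (0% to 0.97%). In a group of 190 it should read 0.53% (0.01% to 2.90%) but would read 0% (0% to 1.92%).

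**The case against.** The strongest case is that this is a labelling matter in one supplementary, descriptive row. The count is wrong only if an event occurs after Month 6 that escapes every open collection route, and the documents give no reason to expect one. The range of 0.50 to 1.00 spans everything from no capture to full capture and rests on an assumed constant hazard. The row does not use the word all, and it names a follow-up period without claiming complete ascertainment. Restricting it to related or fatal events would remove events collected by other routes, so a footnote would be the smaller change. Protocol Section 8.3.1 also tells investigators to report all SAEs and gives no end date in that sentence.

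Some of this stands. The figures are bounds, not predictions. That the row is all-causality is an inference from the missing qualifier, though a firm one beside Month 12 rows that carry one.

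The rest does not rescue the row. Section 8.3.1 ties reporting to the periods in Table 11, treats events outside them as post-study, and says investigators are not obliged to seek them. Events leading to withdrawal have their own table in SAP Section 4.3.2.1, and any other collected event stays in the Month 12 listing, so restricting the row loses no information. A footnote alone would explain the row but would still print an interval on a mixture of fully and selectively collected events.

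**Conclusion.** The inconsistency is real. Followed as written, the SAP prints a Month 12 proportion and exact interval for serious demyelinating disorders without full ascertainment beyond Month 6. The count can only be too low, and it is too low only if an uncollected event actually occurs. Under a constant hazard, the observed share of true events lies between 0.50 and 1.00. With no events, the 12-month upper limit supported by the data lies between 0.97% and 1.92% for a group of 380, and between 1.92% and 3.80% for a group of 190. Only the lower end of each range would be printed. These ranges rest on the constant-hazard assumption and the planned group sizes; the mismatch itself rests on neither. The Month 6 result, the primary and secondary endpoints and the type I error control are unaffected. The point should be corrected before reporting, because it concerns a safety row whose upper limit will be read at face value.

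**What to change.** In SAP Section 4.3.2.1:

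- Tabulate all serious demyelinating disorders to Month 6 only.
- For study end (Month 12), tabulate only those related to the study intervention or fatal, and state that restriction in the table title. This matches the existing SAE and pIMD rows.
- Footnote the listing of SAEs and AESIs to Month 12 with the categories collected after Month 6.

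An optional clarification in SAP Section 6.1.7 would say that the summary of all COVID-19 SAEs ends at Month 6, and that study end applies to AEs leading to withdrawal and to related or fatal SAEs.

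The cost is one SAP sentence, one table title and one listing footnote, plus one clause if Section 6.1.7 is clarified. No additional data collection is needed.

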4.3.2.2. Immunogenicity analysis: humoral immune response

The analysis will be based on the PPS. If, in any group, the percentage of vaccinated participants with serological results excluded from the PPS is more than 5%, a second analysis based on the ES will be performed to complement the PPS analysis.

4.3.2.2.1. *Between groups assessment*

Considering the sampling timepoint at 1-month post-study intervention administration, same analysis as for primary endpoint (refer to Section 4.2.2) will be performed using IU/ml unit for computation of the GMT ratio and SRR difference.

Considering the sampling timepoint at 6-month and 12-month post-study intervention administration, the following analysis will be performed:

- The 2-sided 95% CIs for group GMT ratios (OA-RSV over Adults-HA-RSV group and OA-RSV over Adults-AIR-RSV group) will be derived from an ANCOVA model on \log_{10} -transformed titers for each neutralization assay. The model will include the group and the baseline \log_{10} -transformed titer as covariate. The group GMT ratios will be based on a back transformation of group contrast in the ANCOVA model applied to the logarithmically transformed titers.
- The 2-sided 95% CIs for group SRR difference (OA-RSV minus Adults-AIR-RSV group and OA-RSV minus Adults-HA-RSV group)
- Results will be reported using both ED60 and IU/ml units.

All between groups analyses of secondary endpoints presented in this section will be descriptive with the aim to characterize the difference in immunogenicity between groups. These descriptive analyses should be interpreted with caution considering that there is no adjustment for multiplicity for these comparisons.

4.3.2.2.2. *Within groups assessment*

For each study group, each immunological assay and at each time point that blood samples are collected, the following analysis will be performed:

- a. Percentage of participants with neutralizing titers equal to or above pre-defined assay cut-offs and their 2-sided 95% CIs will be tabulated.
- b. Percentage of participants having a fold increase in neutralizing titers ≥ 4 and their 2-sided 95% CIs will be tabulated.
- c. Unadjusted GMTs and their 95% CIs will be tabulated and displayed graphically.
- d. Furthermore, to account for the multiples timepoints at which the blood samples are collected, a mixed effects model (see Section 4.3.3.1) will be fitted, from which the adjusted GMTs and their 95% CIs will be computed and tabulated.
- e. The kinetics of unadjusted GMTs will be plotted as a function of time for participants with results available at all timepoints.
- f. Unadjusted MGIs and their 95% CIs will be tabulated and displayed graphically.
- g. Distribution of neutralizing titers will be displayed using reverse cumulative curves.
- h. Results will be reported using both ED60 and IU/ml units.

The above mentioned descriptive within group immunogenicity analysis will also be generated by age at vaccination (50-59 YOA, 60-69 YOA, 70-79 YOA and ≥ 80 YOA years) with the exception of analysis described in point d, e and g. No graphical display will be produced.

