4.3.3. Additional considerations

4.3.3.1. Mixed-effects model

For the GMTs calculation based on the mixed effects model mentioned in Section 4.3.2.2, repeated measures analysis of covariance (ANCOVA) model will be fitted including study group (OA-RSV, Adults-AIR-RSV, Adults-AIR-Placebo, Adults-HA-RSV, Adults-HA-Placebo) and post-vaccination visit (Day 31, Months 6, 12), as fixed effects, pre-vaccination log10-transformed titers as a covariate and the response variable is the post-vaccination log10-transformed titers. The PROC MIXED procedure in SAS® will be used to carry out the ANCOVA.

The following SAS codes will be used:

```
PROC MIXED DATA=SERO method=reml empirical;
  CLASS subjID group visit ;
  MODEL post-vac=pre-vacc group visit visit*group/ noint s cl;
  REPEATED visit/ type=un subject=subjID;
  LSMEANS visit*group/ E cl;
  ODS OUTPUT LSMEANS=LS;
  RUN;
```

The above SAS codes may be adapted in case of convergence issues.

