6.2.2.2. Laboratory data

Any missing or non-evaluable immunogenicity measurement will not be replaced. The descriptive analysis performed for each assay at each timepoint will exclude participants with a missing or non-evaluable measurement. This is applicable to the standard way of computing geometric mean titers/concentrations (GMTs/GMCs).

Computation of GMTs/GMCs from the mixed effects model inherently accounts for the missingness, under the assumption that the missing data are missing at random (MAR). Subject having missing pre-vaccination titer will be excluded from ANCOVA and mixed effects models (refer Section 4.3.3.1)

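### Month 6 and Month 12 GMT ratios come from one ANCOVA per visit; contrasts from the repeated-measures model already in the SAP would also use the earlier titers, for a modest gain

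*SAP*

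**What the plan says.** SAP 4.3.2.2.1 opens the later comparisons with "Considering the sampling timepoint at 6-month and 12-month post-study intervention administration, the following analysis will be performed". It then gives the model: "The 2-sided 95% CIs for group GMT ratios (OA-RSV over Adults-HA-RSV group and OA-RSV over Adults-AIR-RSV group) will be derived from an ANCOVA model". On its terms it says "The model will include the group and the baseline" (log10 titer), and on the estimate, "The group GMT ratios will be based on a back transformation of group contrast in the ANCOVA model". There is no visit or participant term, so this is one regression per visit. The section also sets the status of the results: "All between groups analyses of secondary endpoints presented in this section will be descriptive".

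SAP 4.3.2.2.2, point d, introduces a second model for the same titers: "a mixed effects model (see Section 4.3.3.1) will be fitted, from which the adjusted GMTs and their 95% CIs will be computed and tabulated". Its mean structure in SAP 4.3.3.1 is "MODEL post-vac=pre-vacc group visit visit*group/ noint s cl", with an unstructured covariance over Day 31, Month 6 and Month 12. The only output requested is least-squares means by visit and group. SAP 6.2.2.2 adds: "Computation of GMTs/GMCs from the mixed effects model inherently accounts for the missingness", on a missing-at-random assumption.

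Elsewhere, SAP 4.1.1 leaves missing titers unreplaced, and SAP 3 defines PPS membership by timepoint. Under SAP 3.1.3, codes 2090 (sample out of window) and 2100 (no result) remove only the visit concerned. Codes 1040, 1060, 2040 and 2050 remove data from the visit concerned onwards.

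**The concern.** A participant can be in the PPS at Day 31 and out of it at Month 6 or Month 12. The visit-wise ANCOVA discards that participant's earlier titers when it estimates the later ratio, although they carry information about the missing one. The model that would use them is already specified, but it is not asked for the between-cohort contrast.

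Two things are at stake. One is precision. The other is protection if loss depends on the Day 31 response differently in the two cohorts. OA-RSV is open-label, not randomized against Cohort 1, and enrols participants aged 80 and over; Cohort 1 is aged 50-59 and its participants stay blinded to study end. Randomization therefore does not balance loss between the cohorts being compared.

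There is also a presentational cost. The report would show adjusted GMTs from one model and GMT ratios from another for the same groups and visits, and the two will generally not agree.

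**Working it through.** **1. The plan's own figure.** SAP 5 gives 380 enrolled per vaccine group and 10% attrition: 380 × (1 − 0.10) = 342 evaluable, as stated. No rate is given specifically for Month 6 or Month 12. The SD and between-visit correlations come from historical data that are not shown, so everything below rests on assumed values.

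**2. Precision, using Day 31 only.** Let m be the share missing at the later visit and ρ the correlation between Day 31 and the later titer given baseline. If loss is random, the likelihood-based estimate has a confidence interval narrower than that of the ANCOVA by the factor √(1 − ρ²m).

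| m | ρ | √(1 − ρ²m) | CI narrower by |
|---|---|---|---|
| 0.10 | 0.5 | √(1 − 0.025) = 0.987 | 1% |
| 0.20 | 0.7 | √(1 − 0.098) = 0.950 | 5% |
| 0.30 | 0.9 | √(1 − 0.243) = 0.870 | 13% |

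The last row is the edge of the assumed range. A simulation that also used Month 6 (three groups of 342, residual SD 0.40 log10, 20% missing at random) gave intervals 4-8% narrower. It used maximum likelihood and the mean structure of SAP 4.3.3.1 for the three vaccine groups. The SAP code uses REML, empirical standard errors and all five groups.

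**3. Bias, moderate settings.** Assumptions: 342 per group, SD 0.4 log10, baseline correlation 0.5, true ratio 1.00, 1,500 simulated trials per setting, and loss before Month 12 more likely at low Day 31 titer.

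| Loss, OA v Adults | Log-odds per SD | Day 31-Month 12 correlation | ANCOVA ratio | Ratio using Day 31 |
|---|---|---|---|---|
| 15% v 5% | 0.5 | 0.6 | 1.017 | 1.002 |
| 15% v 5% | 0.5 | 0.8 | 1.024 | 0.999 |
| 20% v 10% | 0.8 | 0.6 | 1.027 | 1.003 |
| 20% v 10% | 0.8 | 0.8 | 1.038 | 1.001 |

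The standard error using Day 31 was 0.95-0.99 times that of the ANCOVA.

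For scale, take the 15% v 5% setting. Observed numbers are 342 × 0.85 ≈ 291 and 342 × 0.95 ≈ 325. The residual SD is 0.4 × √(1 − 0.5²) = 0.346. The standard error is 0.346 × √(1/291 + 1/325) = 0.028, and the 95% limits lie a factor 10^(1.96 × 0.028) ≈ 1.13 either side of the estimate. A shift of 1.02 is well inside that.

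**4. Bias, no difference between cohorts.** With random loss, or loss that depends on Day 31 alike in every group, the ANCOVA ratio averaged 0.99-1.01 and the mixed-model ratio 0.98-1.00 (200 runs per setting). The groups are exchangeable in these settings, so departures from 1 are simulation noise.

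**5. Bias, stress case.** If low Day 31 responders drop out preferentially in OA-RSV only (ρ = 0.7), the ANCOVA ratio averages 1.10, 1.18 and 1.25 at 10%, 20% and 30% missing, with coverage of about 76%, 41% and 26%. The mixed-model contrast stays at 1.00-1.01, with coverage of 94-97%.

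**6. Agreement of outputs.** In the 4.3.3.1 model all groups share the baseline slope. The difference between two least-squares means at a visit therefore is the group contrast at that visit. Ratios taken from that model match its adjusted GMTs by construction; ratios from a separate ANCOVA do not.

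**The case against.** The case for leaving the plan alone is substantial.

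- The Month 6 and Month 12 ratios are not listed endpoints. The secondary humoral endpoint is the GMT per group and timepoint, and mixed-model estimates of it are already planned. Dividing two of them gives the MAR-based point ratio; only its interval is missing. This stands and limits the weight of the point.
- The ratios carry no margin, alpha or decision rule. This stands.
- SAP 4.3.2.2 adds an Exposed Set analysis if more than 5% of vaccinated participants with serological results are excluded from the PPS in any group. That can restore out-of-window and other excluded results. It cannot restore samples never taken, so it answers the point only in part.
- Using the Day 31 ANCOVA at every visit keeps the ratios comparable over time. This stands, and is the reason to keep it alongside.
- The 4.3.3.1 model has one baseline slope for all visits. A baseline-by-visit term deals with that. The slope and covariance would still be shared with the placebo groups, and the retained ANCOVA would show whether that matters.
- A joint model refitted with Month 12 data may shift the Month 6 contrast slightly after the Month 6 analysis. The footnote in SAP 4.7.1 already tolerates slight differences between successive analyses.

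A reader might also infer that the SAP adopts the mixed model as its missing-data strategy and then contradicts itself. The documents do not support that. SAP 4.3.2.2.2 introduces the model to account for multiple timepoints, SAP 4.1.1 makes non-replacement the general rule, and SAP 6.2.2.2 mentions MAR as a property of the additional model.

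**Conclusion.** The point holds as a minor, nearly free improvement to a descriptive analysis. It is not an error. The later ratios leave valid earlier PPS titers unused, and the readable text gives no reason for not requesting contrasts from the model that would use them (parts of the SAP are redacted).

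Under moderate assumed loss and correlation, the gain is an interval about 1-5% narrower, plus protection against a bias of about 1.02-1.04 that arises only if loss related to the Day 31 titer differs between cohorts. All these sizes rest on assumed SD, correlation and attrition.

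A reader might infer that the planned persistence ratios are biased, or take 1.10-1.25 as the expected size. Neither is supported: the documents give no sign of differential loss by Day 31 response, and those figures come from a deliberately one-sided scenario. Nor does the point touch the confirmatory Day 31 analysis, the non-inferiority conclusions or type I error.

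**What to change.** In SAP 4.3.3.1, add a baseline-by-visit term to the repeated-measures model. From that same model, request the OA-RSV minus Adults-HA-RSV and OA-RSV minus Adults-AIR-RSV contrasts at Month 6 and Month 12, back-transformed with 95% CIs. That is 2 comparisons × 2 visits × 2 assays = 8 ratios, in each reporting unit. A separate model for the ratios would bring the mismatch with the adjusted GMTs back.

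In SAP 4.3.2.2.1, name these contrasts as the source of the Month 6 and Month 12 ratios, and keep the visit-wise ANCOVA alongside for comparability with Day 31. State that, for exclusions under codes 1040, 2040 and 2050, the model targets a hypothetical value under MAR: the titer had the forbidden vaccine, forbidden medication or intercurrent condition not occurred.

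The cost is SAP wording and a few lines of code, with no new data. The one downside is that Month 6 contrasts may move slightly when the model is refitted with Month 12 data. If those analyses have already been run, the contrasts can be added and labelled supportive.
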